This study's primary objective is to test the hypothesis that a single infusion of subcutaneous lidocaine can cause a clinically useful reduction in cancer pain within 48 hours of infusion and lasting a minimum of 7 days. A clinically useful reduction in pain is defined by either a 2-point reduction (on a 0-10 scale) in the worst pain experienced over a 24-hour period, or a $\geq 30\%$ reduction in 24-hour opioid requirement. We will use a composite endpoint of reduction in pain without increase in 24-hr opioid requirement or no decrease in pain with a $\geq 30\%$ reduction in 24-hour opioid requirement.

The secondary objectives are 1) to determine whether any significant toxicities occur as a result of the infusion. For this study significant toxicity is considered as any adverse event which either leads to the infusion being terminated, or which leads to medical intervention, such as prescribing of another medication or equivalent treatment, 2) to determine the effect of Lidocaine infusion on QOL parameters as measured by the Patient Outcome Scale (POS) Questionnaire and 3) to determine the duration of response to lidocaine infusion.

Eligibility criteria:

Male or female patients 18 years of age or older
In or outpatients referred to the BCCA PSMPC Clinics with a diagnosis of cancer
Subjects must have somatic, visceral or neuropathic pain related to cancer
Pain intensity, measured by a worst pain score over the last 72 hours of ≥ 4 on a 0-10 numerical rating scale
Must have tried at least one opioid medication without adequate response or with significant side-effects for at least one week
For those with neuropathic pain, must have also tried at least one adjuvant analgesic, such as a tricyclic (unless contraindicated) or an anticonvulsant without adequate response or with significant side-effects for at least one week
Life expectancy of > 3 months
Must be able to communicate symptoms indicating potential toxicity of Lidocaine
Must have a competent caregiver in the home overnight after each infusion
Must be willing to remain within 30 minutes of the Cancer Centre during each infusion

Exclusion criteria:

Clinically significant cardiac disease, i.e, cardiac failure, atrial fibrillation with slow ventricular rate (<60), any degree of heart block

New analgesic treatment initiated in time frame which might have effect within one week of study drug.

Hyper or hypokalemia.

Liver failure (bilirubin ≥ 25 μ mol/L).

Renal failure (eGFR <50% of normal)

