At 1000 am on Day 2 and Day 3, the BPI and POS will be completed. If there is a reduction in pain scores, the BPI and POS will continue to be completed on Day 7, 14 and 21 post each infusion, or until the worst pain score on the BPI #3 has returned to baseline. If there is no change, the questionnaires for Day 7 will be completed and the patient will be scheduled for the next follow up visit and treatment within a minimum of 48 hours and maximum of three weeks of the pain returning to baseline. The Medication Use Log is to be completed daily, and the Adverse Events Log completed if an adverse event occurs. Telephone contact will be made at a minimum twice a week until the pain is back to the pre-treatment level by the research nurse or physician and to adjust medications if necessary, and, once pain returned to baseline, once weekly telephone contact will be done til the 2nd treatment visit to review any condition or medication changes. Subjects will also be encouraged to call the physician at any time if they experience any adverse event or to report return to baseline pain score.

Once the worst pain score on the BPI (question #3) has returned to baseline and at least 48 hours have elapsed, the second treatment will be arranged. If there is a response the patient will continue with diaries and questionnaires weekly until the BPI score returns to baseline

Second Treatment Visit

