This will be arranged within a minimum of 48 hours and maximum of three weeks of the pain returning to baseline but will be no earlier than 48 hours after the 1st treatment. The baseline weight will be used to determine the dose for the second treatment. At 1000 am on Day 2 and Day 3 post second treatment, the BPI and POS will be completed. If there is a reduction in pain scores, the BPI and POS will continue to be completed on Day 7, 14 and 21 post each infusion, or until the worst pain score on the BPI #3 has returned to baseline, at which time the end of study visit will be arranged within a minimum of 48 hours and a maximum of three weeks of the pain returning to baseline. If there is no change, the questionnaires for Day 7 will be completed and the patient will be scheduled for the end of study visit within a minimum of 48 hours and maximum of three weeks of the pain returning to baseline. The Medication Use Log is to be completed daily, and the Adverse Events Log completed if an adverse event occurs. Telephone contact will be made at a minimum twice a week until the pain is back to the pre-treatment level. Subjects will also be encouraged to call the physician at any time if they experience any adverse event or to report return to baseline pain score.

Final Visit Post Second Infusion (once the worst pain score on the BPI (question #3) has returned to baseline by phone assessment and at least 48 hours or a maximum of three weeks of the pain returning to baseline., At this visit subjects will again complete the Brief Pain Inventory and POS and their Medication Use Log and Adverse Events Log will be reviewed. This will be the end of the study.

Outcome measures:

Primary:

The primary outcomes measure is a binary variable indicating whether lidocaine caused a reduction in cancer pain within 48 hours of infusion and lasting a minimum of 7 days. Lidocaine will be considered to have caused reduction in cancer pain if the subject had either one of the following episodes lasting a minimum of 7 days:

- 1) A 2-point reduction in severity of pain as assessed by the worst pain score in the last 24 hours (question 3) of the Brief Pain Inventory – Short Form (BPI), compared to the BPI pain score at baseline.

Or:

- 2) ≥30% reduction in 24-hour opioid dose.

The duration of the pain reduction is measured by weekly BPI pain scores.,

Secondary:

- 1) Incidence and severity of adverse events.

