Final Visit: (post 2nd infusion, once the worst pain score on the BPI (question #3) has returned to baseline by phone assessment and minimum 48 hours and a maximum of three weeks since the return to baseline., At the final visit, the ,BPI, POS, Medication Use Log. Adverse Events Log and PPS will be reviewed

A positive response re: pain relief would be defined as any of the following:

- A 2-point reduction in worst pain intensity (#3 on the BPI) within 48 hours of infusion and lasting a minimum of 7 days
- Reduction in analgesic dose by greater or equal to 30% will also be considered an indicator of positive response.

Statistical Considerations: **Objective**

To compute the power and sample size calculation for the study

Assumptions

- Probability of response in the placebo group = 30%
- There is no carry-over effect, no period effect and no sequence effect in the study

- 0.01% of the patients who did not respond to the lidocaine will respond to the placebo

Null Hypothesis: There is no difference between a single infusion of subcutaneous lidocaine and the placebo

Alternative Hypothesis: A single infusion of subcutaneous lidocaine can cause a reduction in cancer pain

Sample Size / Interim Analysis

A sample size of 40 patients achieves 84% power to detect a 20% difference at a 2.5% significance level using a one-sided McNemar's Test, under the assumptions that 30% of the patients respond to the placebo and 0.01% of the patients who do not respond to the lidocaine will respond to the placebo. This sample size is increased to 50 patients to account for a 20% drop-out rate. This drop-out rate is based on our experience accruing similar patients to studies. The sample size methodology is based on the methodology described in Lachenbruch 1992.

We have demonstrated in the completed Feasibility Study for a Randomized Double Blind Placebo Controlled Crossover Trial of the Use of Subcutaneous Lidocaine Infusion for Chronic Cancer-related Pain that recruitment to such a study is feasible, and that we should expect this study to take 6 months for accrual.

An interim analysis will be carried out after 20 patients have completed the study to allow the trial to be stopped early for demonstrated efficacy. One-sided McNemar's tests will be carried out to test whether a single infusion of subcutaneous lidocaine will cause a reduction in cancer pain for both the interim and final analyses at the p-values of 0.00153 and 0.02347 respectively.

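### Adverse events have no common counting window: follow-up and scheduled enquiry lengthen with the response, so unrelated events are likely to be modestly over-counted after the infusion that works

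*Combined protocol and SAP*

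**What the plan says.** Study Objectives (secondary objective 1) asks whether significant toxicity is caused by the infusion. It defines such toxicity as "any adverse event which either leads to the infusion being terminated, or which leads to medical intervention", and Notes on Outcome Measures repeats the definition. Neither place sets a time limit or says how cause is to be judged. The listed safety outcome is "Incidence and severity of adverse events", with no window or denominator. Statistical Considerations contains no adverse-event analysis.

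Follow-up length depends on response. Between Visits and Second Treatment Visit place the next treatment, or the final visit, 48 hours to three weeks after pain returns to baseline. Responders continue questionnaires until that return; non-responders need them only on Days 2, 3 and 7.

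Contact also depends on response. Between Visits states: "Telephone contact will be made at a minimum twice a week until the pain is back to the pre-treatment level". Schedule of Assessments names adverse events as a topic of these calls. Afterwards, "once pain returned to baseline, once weekly telephone contact will be done til the 2nd treatment visit", and those calls review changes in condition or medication. For the time after return to baseline in period 2, no call frequency is given.

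Several elements do not depend on response: infusion-day monitoring, calls on Days 2 and 3, an Adverse Events Log filled in whenever an event occurs, review of that log before each infusion and at the final visit, and an open invitation to call.

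**The concern.** In patients with cancer, many events that lead to a prescription have nothing to do with a 5.5-hour infusion. Their number grows with the time observed, and here that time grows with efficacy. The crossover does not cancel this, because a patient who responds to one infusion and not the other has two windows of different length. The twice-weekly calls also serve to adjust medication, so one contact can both detect an event and produce the intervention that makes it significant.

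If lidocaine works, a plain tabulation of incidence by treatment would mix drug toxicity with longer observation. If placebo responses lasted longer, the error would run the other way. At stake is the reading of secondary objective 1, not the primary analysis.

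**Working it through.** **The plan's own figure.** The documents state no number for toxicity. The response rates come from the sample-size paragraph, so that was checked first. The plan says "A sample size of 40 patients achieves 84% power to detect a 20% difference at a 2.5% significance level using a one-sided" McNemar test, with 30% responding to placebo (hence 50% to lidocaine) and "0.01% of the patients who did not respond to the lidocaine will respond to the placebo".

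- Placebo-only responders: 0.0001 × 0.50 = 0.00005. Lidocaine-only responders: 0.20 + 0.00005 = 0.20005.
- Exact conditional McNemar power with 40 pairs is 83.8%, which agrees with 84%. For drop-out, 40/0.80 = 50.

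The sample size stands. About 20% of patients are expected to respond to lidocaine alone.

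**Observation window.** Let D be the response duration and G the gap from return to baseline to the next treatment or final visit.

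- D: 7 days (the minimum for a response), 9.3 days (mean in the cited intravenous cancer trial, Human studies), 15–21 days (Clinical Experience, subcutaneous).
- G: 2 to 21 days.
- Responder window = D + G. Non-responder window = max(G, 7); the 7-day floor, from the Day 7 questionnaires, is an assumption. D is assumed the same on either treatment.
- Mean window: lidocaine 0.5 × responder + 0.5 × non-responder; placebo 0.3 × responder + 0.7 × non-responder.
- Scheduled calls: 2D/7 + G/7 for a responder, max(G, 7)/7 for a non-responder. The Day 2 and 3 calls, equal on both treatments, are left out.

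| D | G | Responder / non-responder (days) | Mean lidocaine / placebo (days) | Window ratio | Call ratio |
|---|---|---|---|---|---|
| 7 | 2 | 9 / 7 | 8.0 / 7.6 | 1.05 | 1.19 |
| 7 | 21 | 28 / 21 | 24.5 / 23.1 | 1.06 | 1.11 |
| 9.3 | 7 | 16.3 / 7 | 11.7 / 9.8 | 1.19 | 1.30 |
| 18 | 7 | 25 / 7 | 16.0 / 12.4 | 1.29 | 1.40 |
| 18 | 21 | 39 / 21 | 30.0 / 26.4 | 1.14 | 1.23 |
| 21 | 7 | 28 / 7 | 17.5 / 13.3 | 1.32 | 1.43 |

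Across D = 7–21 and G = 2–21 the window ratio runs from 1.05 to 1.32 and the call ratio from 1.11 to 1.43.

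**Incidence with no drug toxicity.** Assume λ intervention-requiring events per patient-day, the same on both treatments. The documents give no rate, so λ = 0.005 to 0.03 was tried. The chance of at least one event is 1 − exp(−λ × window). The treatment difference is 0.2 × [exp(−λ × non-responder window) − exp(−λ × responder window)].

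| λ | D, G | Lidocaine | Placebo | Difference (points) |
|---|---|---|---|---|
| 0.005 | 7, 2 | 3.9% | 3.7% | 0.2 |
| 0.005 | 7, 21 | 11.5% | 10.9% | 0.6 |
| 0.01 | 9.3, 7 | 10.9% | 9.2% | 1.7 |
| 0.01 | 18, 7 | 14.4% | 11.4% | 3.1 |
| 0.01 | 18, 21 | 25.6% | 22.9% | 2.7 |
| 0.02 | 18, 7 | 26.2% | 20.9% | 5.3 |
| 0.03 | 21, 7 | 37.9% | 30.3% | 7.6 |

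Risk ratios run from about 1.04 to 1.30. With the shortest response and gap (7 and 2 days) the difference stays below 1 point at every λ tried.

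**Visibility in one trial.** In a paired simulation of 40 patients (D = 18, G = 7, λ = 0.02), lidocaine shows the higher count in 67% of trials and placebo in 24%; the rest tie. A one-sided 2.5% paired test, which the plan does not contain, would falsely flag lidocaine in about 4.5% of trials, against about 1% with a fixed 7-day window.

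**After the change.** With a window of 2 days on both treatments, background incidence is 1 − exp(−2λ): 1.0%, 2.0%, 3.9% and 5.8% for λ = 0.005, 0.01, 0.02 and 0.03. It is the same after lidocaine and placebo.

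**The case against.** Several points for the plan stand.

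- Objective 1 already confines toxicity to what the infusion causes. A reader might infer that the plan has no attribution requirement; it has one, and lacks only a procedure. Blinded attribution, properly applied, would remove most late unrelated events.
- Events that end the infusion fall within its 5.5 hours and cannot be inflated.
- The event-driven log, its scheduled reviews and the Day 2 and 3 calls limit differential questioning. The weekly calls ask about medication changes, which bears directly on the medical-intervention limb. These safeguards do not equalise observation time.
- Notes on Outcome Measures expects fewer side-effects when responders take less opioid. This could offset part of the bias. The documents give no figure for it, so it is not in the arithmetic.
- No between-treatment toxicity test is planned, so no formal conclusion is at risk.

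A reader might also infer a large distortion by following one patient who responds only to lidocaine, with 18 days after it and 7 after placebo. At one background event per 60, 30 or 15 days, that patient's chance of an event is 26% against 11%, 45% against 21%, or 70% against 37%. The documents do not support reading this as the treatment contrast. Such patients are about 20% of the sample; averaged over everyone, the same inputs give 18.5% against 15.5%, 33.0% against 28.1% and 53.6% against 47.1%. The 18 days also comes from a pain clinic with largely non-cancer experience. With 9.3 days and the gap left out, mean windows are 8.15 and 7.69 days, an excess of 6%.

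**Conclusion.** The point holds as a modest, correctable weakness in a secondary outcome. Followed as written, the plan compares adverse-event incidence over unequal windows whose length depends on response, and it schedules more enquiry during the response. If lidocaine works, unrelated events needing intervention are likely to be over-counted after it. The mean window is about 1.05 to 1.3 times that of placebo, and incidence differs by under 1 to about 8 points with no drug effect.

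These sizes rest on the plan's 50% and 30% response rates, the durations it cites, a 7-day floor for non-responders, equal response duration on both treatments, and background rates that are assumed. The direction is an expectation: a given trial can go the other way, and lower opioid use may reduce the shift. The documents do not support saying that lidocaine is bound to look more toxic, or that the primary analysis or sample size is affected.

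**What to change.** Before unblinding, state in Outcome measures and Statistical Considerations that:

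1. The main lidocaine–placebo safety comparison covers start of infusion to 48 hours, for all adverse events and for significant toxicity. Second Treatment Visit guarantees this interval, since the second infusion comes no sooner than 48 hours after the first. Infusions start at 0900–0930, so with the infusion day as Day 1 the 10:00 Day 3 questionnaires fall at about 48.5–49 hours; Schedule of Assessments also has Day 2 and Day 3 calls after each infusion. A 7-day window would catch more, but the 48-hour minimum does not guarantee it.
2. All later events are reported separately by treatment, as events per patient-day, with the investigator's relatedness judgment made blind. The per-day rate corrects for length of observation but not for call frequency, and the report should say so.

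The cost is definition and analysis wording plus one relatedness field on the form. No visit, call or sample-size change is needed. The downside is that late events, including those during opioid re-adjustment after a response, leave the headline incidence, though they are still reported.

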Subjects will remove their Holter monitor 4 hours after completion of infusion and will return the monitor as instructed according to site, for analysis the following day. The monitor tracings will be reviewed independently. The Holter monitors will be made available from the Cardiology Depts. at Vancouver General Hospital and Kelowna General Hospital, as well as Lifelabs in Prince George.

Subjects will be allowed to use breakthrough pain medications as needed during the study period. These doses will be documented.

Between Visits

Subjects' short-acting opioid consumption will be assessed by telephone after the infusions, and those who respond will re-start their long-acting opioid at a dose determined by their use of short-acting opioid and current pain experience. Those who have not responded will resume their prior long-acting and breakthrough opioid doses as prior to the infusion and have their next treatment within a minimum of 48 hours and maximum of three weeks of the pain returning to baseline... Pain control will be maintained between the infusions by the same opioid consumption as at baseline, including breakthrough as needed, and returning to the subject's prior opioid dosing regimen as soon as any effect of the infusion is perceived to have worn off. Long-acting opioid dosing will only be reduced if the patient feels they have sufficiently improved pain control following an infusion, so there will be no risk of confounding the study results or making pain worse. As noted in the eligibility/exclusion criteria, no new adjuvant analgesic (non-opioid medication) or procedure which may have an analgesic effect will be started or stopped during the study.

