Prior to the First Scheduled Treatment:

Medication Use Log use for three days prior to the first treatment visit

Day 1 pre each infusion:

BPI, POS, and Medication Use Log, review of Adverse Events Log, vital signs, attach Holter Monitor. The Holter Monitor will record for the duration of each infusion plus 4 hours subsequently, and will be removed by the patient.

During each infusion:

Vital signs will be measured and the infusor will be inspected every 15 minutes for the 1st hour, halfway through the infusion and on completion; the physician will be contacted ASAP if the pulse drops to less than 60 beats per minute or increases to over 100 beats per minute, or the PaO₂ falls below 90%; systolic BP changes by 25mm from pre-treatment BP. Patients will be given a Medicaton Log and an Adverse Event Log to keep track of any A/Es they experience.

In the hour prior to completion of each infusion (i.e. 4.5 to 5.5 hours since started: no later than between 2.00 and 3.00pm):

A lidocaine blood level will be drawn at the appropriate BCCA laboratory and the subject's vital signs will be taken. Blood will be analysed at the Provincial Toxicology Lab, Vancouver

At the end of each infusion on Day 1:

BPI, POS, Medication Use Log, assessment of toxicity via Adverse Events Log and vital signs.

At each of the intervals where the vital signs are to be taken, the patient's pain score will be assessed and recorded and the infusion site will be assessed to ensure the medication is infusing properly

Daily During Study:

Medication Use Log

Subjects encouraged to call study physician if any concerns
On day 2 and 3 after each Infusion and at least twice a week
or until pain is back to pre-treatment level

Phone call by physician or study nurse to review opioid dosing, adverse events and subject's perception of pain relief

Once pain returned to baseline, once weekly telephone contact will be done til the 2nd treatment visit to review any condition or medication changes

At 10.00am on Day 2 and Day 3 post each infusion, BPI and POS Questionnaires to be completed.

If there is a response to the treatment, the patient will also complete them on Day, 7, 14 and 21, or until the worst pain score on the BPI #3 has returned to baseline . If there is not a response , the BPI and POS Questionnaires will only be required for Day 2, 3 and 7.

Daily

Medication Use Log to be completed and Adverse Events Log if subject experiences symptoms or side-effects

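### Minor: the 48-hour floors for the second infusion are shorter than the 7-day primary window and ignore its opioid limb, so an occasional opioid response could be cut short

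*Combined protocol and SAP*

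**What the plan says.** **Opening of the second period.** Under Between Visits, "Once the worst pain score on the BPI (question #3) has returned to baseline and at least 48 hours have elapsed, the second treatment" can be arranged. Second Treatment Visit gives a range of 48 hours to three weeks from the return of pain to baseline and adds that the treatment "will be no earlier than 48 hours after the 1st treatment". The final visit follows the same 48-hour-to-three-week rule. Opioid dose is not part of either rule.

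**Primary outcome.** Under Outcome measures, lidocaine counts as effective "if the subject had either one of the following episodes lasting a minimum of 7 days": a 2-point fall in worst pain, or a reduction of at least 30% in 24-hour opioid dose. Onset must be within 48 hours of infusion. Study Objectives makes the opioid limb independent of pain: "We will use a composite endpoint of reduction in pain without increase in 24-hr opioid requirement or no decrease in pain with a" reduction of at least 30% in that requirement. Notes on Outcome Measures gives the reason: some patients may tolerate the same pain on much less opioid.

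**Provisions that narrow the gap.**
- Under Between Visits, patients whose pain falls continue the forms on Days 7, 14 and 21, "or until the worst pain score on the BPI #3 has returned to baseline". For the others, "If there is no change, the questionnaires for Day 7 will be completed" and the next treatment is then scheduled.
- Schedule of Assessments says that, without a response, "the BPI and POS Questionnaires will only be required for Day 2, 3 and 7".
- On opioids, "Pain control will be maintained between the infusions by the same opioid consumption as at baseline", and the prior regimen is resumed once the effect is felt to have gone.
- The Medication Use Log is kept daily, and telephone calls review medication.

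**The concern.** Worst pain at baseline does not show that a response is over, because the outcome can be met by an opioid reduction alone. The crossover rule nevertheless treats the return of pain as the end of the first period, and both of its floors are shorter than the 7 days that the outcome needs.

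The patient at issue has early pain relief, cuts opioid by at least 30%, sees worst pain return to baseline by about Day 5, stays on the lower dose and is booked near the earliest date. For that patient the first-period opioid outcome is cut short, or its last days are mixed with the effect of the second infusion. The daily log shows the dose up to re-infusion, but it cannot show a full episode free of the second drug. The treatment-order score test in Statistical Considerations may flag an order effect afterwards; it does not recover the lost outcome.

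**Working it through.** **1. Timing.** Take the infusion day as Day 1, as the Schedule of Assessments does. The plan does not say when the 7 days start. Counted from the infusion, they end on Day 8. Counted from an onset at the 48-hour limit (Day 3), they end on Day 10. For a patient whose pain first fell, earliest re-infusion = day pain is back at baseline + 2 days.

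| Pain back at baseline | Earliest re-infusion | Short of Day 8 | Short of Day 10 |
|---|---|---|---|
| Day 3 | Day 5 | 3 days | 5 days |
| Day 4 | Day 6 | 2 days | 4 days |
| Day 5 | Day 7 | 1 day | 3 days |

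Only the Day 3 row rests on a scheduled BPI. None is scheduled between Day 3 and Day 7, so the other rows rest on telephone reports.

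**2. The plan's own power.** Inputs from Statistical Considerations: 30% response on placebo, a 20-point difference (so 50% on lidocaine), 0.01% placebo response among lidocaine non-responders, 40 pairs, final one-sided level 0.02347.
- p01 (placebo only) = 0.0001 × 0.50 = 0.00005
- p10 (lidocaine only) = 0.20 + 0.00005 = 0.20005
- p11 (both) = 0.30 − 0.00005 = 0.29995

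The exact McNemar test rejects when P(Bin(a + b, ½) ≥ a) ≤ 0.02347, where a and b are the two discordant counts. Summing the trinomial probabilities of all rejecting (a, b) gives 83.8% at 40 pairs, and the same at 0.025. This reproduces the stated 84%. At 50 pairs the figure is 95.2%.

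**3. How many patients.** With 20 pairs in each order, first-period responders = 20 × 0.50 + 20 × 0.30 = 16. The documents give no share affected. Assume g = 1%, 2% or 5%: 16g = 0.16, 0.32 or 0.80 of a patient.

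**4. Effect if all of them are scored as non-responders.** With half the patients in each order and the same g on both treatments:
- p10′ = p10 + ½g(p11 − p10)
- p01′ = p01 + ½g(p11 − p01)
- difference = 0.20 − 0.10g

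| g | Difference (points) | Power, 40 pairs | Power, 50 pairs |
|---|---|---|---|
| 0 | 20.0 | 83.8% | 95.2% |
| 1% | 19.9 | 82.3% | 94.1% |
| 2% | 19.8 | 80.8% | 93.0% |
| 5% | 19.5 | 76.3% | 89.4% |

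If they are scored as responders on the shortened log, every row equals the first.

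**5. Sensitivity.** Part of the fall reflects the near-zero p01, which makes any added reverse discordance costly. At 40 pairs and g = 5%, the plan's inputs lose 83.8 − 76.3 = 7.5 points. With p01 = 2% and p10 = 22% the loss is 70.6 − 65.0 = 5.6 points. With p01 = 5% and p10 = 25% it is 56.2 − 52.4 = 3.8 points.

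**6. Direction.** If the shares differ by treatment, lidocaine loses ½ × 0.50 × gL and placebo loses ½ × 0.30 × gP. The shift is against lidocaine unless gP exceeds 0.50/0.30 = 1.67 times gL.

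**The case against.** The strongest reply is that the other provisions nearly close the path. Patients with no change in pain, the main group for whom the opioid limb was written, are told to complete Day 7 forms before the next treatment is scheduled. A patient whose pain relapses by Day 5 has no 7-day pain response, so the Schedule of Assessments can be read as requiring Day 7 forms there too, and a Day 7 form makes little sense after a Day 5 infusion. Staff aim to restore the prior opioid dose and telephone regularly, and booking may be as late as three weeks after pain returns.

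Most of this stands, and it is why the case is uncommon. It does not close the gap. Between Visits lets a patient whose pain fell stop the forms once worst pain is back at baseline. Opioid restoration depends on a perceived loss of effect, which a patient content on a lower dose may not report. Once pain is back, calls drop to weekly, so a medication review need not fall within the 48 hours. None of these provisions sets a 7-day minimum or an opioid condition.

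The size of the effect is also fairly challenged. The 1% to 5% share has no source in the documents, and it is applied to all first-period responders although the path needs several things to coincide.

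A reader might infer that patients in general can be crossed over at 48 hours before their outcome is known. The Day 7 instruction for patients with unchanged pain does not support that reading.

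**Conclusion.** A minor inconsistency. The crossover floors do not match the length or the content of the primary outcome, and one narrow route leaves a first-period opioid response unobservable. On the assumed shares, fewer than one patient in 40 is affected and the treatment difference moves by 0.1 to 0.5 points. Any bias is against lidocaine, given similar shares on both treatments and scoring as non-responders; the plan does not say how such patients would be scored.

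A reader might take the power table as evidence that the sample size is wrong, or that the trial risks a false-positive result. Neither follows. The 84% reproduces, and the lower figures need an unsourced share and a scoring rule that the plan does not state. The 76% also needs the top of the assumed range together with near-zero reverse discordance.

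The documents also do not name the reference dose for the 30% opioid reduction. That is a separate missing detail, and this verdict does not rest on it.

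**What to change.** In Second Treatment Visit, replace the floor in "will be no earlier than 48 hours after the 1st treatment" with one that covers the whole primary window, and align the sentence under Between Visits with it. The floor should be Day 10 (48-hour onset limit plus 7 days), or Day 8 if the plan states that the 7 days run from the infusion. A Day 8 floor without that statement would still cut short an episode that begins at the permitted 48 hours.

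For every patient in both periods, require the Day 7 BPI and the daily Medication Use Log through the end of that window before the second infusion or the final visit. Amend Schedule of Assessments to match.

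The cost is a few sentences and, for a few patients, some extra days between infusions. For pain back at baseline on Day 3, the three-week limit runs to Day 24, so Day 10 fits well inside it. No new visit, test or sample size is needed.
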